6.6.2. Reporting of Pharmacokinetic Concentrations for Descriptive Statistics

The PK analyst will appropriately flag and annotate treatment of any anomalous concentrations, exclusions and any special treatment for descriptive statistics and plots. BGB-DXP593 concentration and time data will be listed individually and summarized by dose level using descriptive statistics.

The following conventions will be used for reporting descriptive statistics for concentration data.

- PK concentrations should be reported in listings at the same level of precision as that in the source data.
- If a concentration at a given time point is below the assay quantification limit (BLQ), the concentration shall be reported as the term "BLQ" with the lower limit of quantitation (LLOQ) defined in the footnotes. BLQ values shall be treated as zero for computation of descriptive statistics.
- If a concentration at a given time point is missing it shall be reported as a missing value. Missing values may be defined in a bioanalytical source as "NS" (no sample), "NR" (no result), "IS" (insufficient sample), etc. If missing data are not identified in the bioanalytical source (i.e., the record is missing), the reporting convention of "NS" shall be utilized.
- If the calculated mean concentration is BLQ, the mean value shall be reported in outputs (such as tables) as BLQ and SD and CV% shall be reported as ND (not determined). Minimum, median, and maximum may be reported.

BeiGene

6.6.3. Plots of Pharmacokinetic concentrations

BGB-DXP593 concentration versus time data will be plotted individually and summarized graphically using arithmetic mean (±SD) plots by dose level. Arithmetic mean concentrations that are BLQ shall be set to zero for plotting on both linear scale and log-linear scale.

6.6.4. Reporting of PK Parameters for Descriptive Statistics

The PK analyst will appropriately flag and annotate treatment of any anomalous PK parameters, exclusions and any special treatment for descriptive statistics.

- All the PK parameters except t_{max} should have at least the following summary statistics: sample size (n), mean, standard deviation (SD), coefficient of variance (CV%), median, minimum, maximum, geometric mean, geometric CV%; t_{max} should be presented as median, range (minimum, maximum), and sample size (n) when presenting the summary statistics.
- Geometric mean (geometric CV%) will be the default method of reporting PK parameters within in-text tables.
- For any parameters that $n \le 2$, SD should not be presented.
- The units for all PK parameters will be provided.
- It is recognized that the number of decimals in reported concentrations, for example: "9632.94401 ng/mL" or "9.963294401 ug/mL" are highly improbable and will be queried (since bioanalytical assays generally do not have this level of precision). Usually the first-in-human dose escalation trial will provide the numerical range of PK parameters e.g. AUC range from 10 to 10,000 ng.hr/mL and C_{max} range from 1 to 1000 ng/mL.

In this scenario, for reporting PK parameters such as AUC and C_{max}, the following guidance is provided for rounding:

- If the numerical value is below 100 then one decimal place may be used e.g. 0.1 or 99.9.
- For values ranging from >100, whole numbers should be used e.g. 100 or 9999.
- If > 10,000 the clinical pharmacologist may decide on changing units e.g. from μg/ml to mg/ml.
- For reporting times e.g. for t_{max} or $t_{1/2}$, if <1 hr use 2 decimals; time up to 24 hr should be reported to one decimal place e.g. 23.5 hr, time >24 hr should be rounded to nearest whole number e.g. 105 hr.

6.6.5. Software

For the calculations of PK parameters Phoenix® WinNonlin® Version 7.0 or higher (Certara, NJ. USA) will be used.

BeiGene 12 May 2021

6.7. Immunogenicity Analyses

The scope of anti-drug antibodies (ADA) calculations used for characterizing clinical immunogenicity depends on the incidence and kinetics of detected (ADA). Therefore, not all parameters described below may be derived.

The immunogenicity results will be summarized using descriptive statistics by the number and percentage of subjects who develop detectable ADAs. The incidence of positive and neutralizing ADAs will be reported for ADA-evaluable subjects according to the following definitions:

- ADA-evaluable subject: Number of subjects with reportable non-missing baseline result
 and at least one reportable sample taken after drug administration during the treatment or
 follow-up observation period with reportable result (used for computing treatmentinduced ADA incidence).
- Treatment-emergent ADA: Treatment-boosted ADA subject or treatment-induced ADA subject. Synonymous with "ADA Incidence".
- Treatment-induced ADA: ADA-evaluable subjects that were ADA-negative at baseline and ADA-positive following administration of biologic product.
- Treatment-boosted ADA: Baseline-positive ADA-evaluable subject with significant increases (4-fold or higher) in ADA titer after biologic drug administration. [Baseline-positive ADA-evaluable subject: an ADA-evaluable subject with positive ADA result].
- Persistent ADA: Treatment-induced ADA detected at two or more sampling time points during the treatment (including follow-up period if any), where the first and last ADA-positive samples (irrespective of any negative samples in between) are separated by a period of 16 weeks or longer.
- Transient ADA: Treatment-induced ADA detected only at one sampling time point during the treatment or follow-up observation period, or two or more time points during the treatment, where the first and last ADA-positive samples are separated by a period of less than 16 weeks, and the subject last sampling time point is ADA-negative.
- Neutralizing ADA: subjects with positive NAb.

The immunogenicity results will also be listed.

Additional ADA analyses (such as the effect of immunogenicity on PK, and safety) may be conducted if deemed necessary and will be described in a separate analysis plan.

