1.3.2.1. Allometric Scaling for Human Pharmacokinetics Projection

Serum concentration-time profiles from 36 cynomolgus monkeys that received either a single dose of BGB-DXP593 at 10 mg/kg or repeated doses of BGB-DXP593 at 30 mg/kg, 100 mg/kg, or 300 mg/kg once every 2 weeks for 2 doses (Section 1.2.1.2) were used in a population PK analysis with NONMEM[®] Version 7.3 (ICON plc; Dublin, Ireland).

A 2-compartment model with first-order elimination described the PK data well. Between animal variability was estimated for clearance (CL) and volume of distribution (V_z). A proportional error model was used. Human PK parameters were obtained by scaling respective cynomolgus monkey PK parameters multiplied by the ratio of body weight (human to monkey) and taken to the power of 0.75 for clearance and intercompartmental clearance and 1.0 for the central and peripheral compartment volumes ([Mahmood and Balian 1999](#)).

The serum concentration-time profiles in humans for BGB-DXP593 were simulated using software R Version 3.4.4 (Figure 1). The cynomolgus monkey PK parameters and projected human PK parameters are shown in Table 1.

Figure 1: Simulated BGB-DXP593 Serum Lung (Assuming 1% Biodistribution) Concentration-Time Profiles in Humans

Abbreviation: IC₉₉, concentration of BGB-DXP593 required to achieve 99% inhibition of host cell infection in vitro in an authentic virus neutralization assay

Notes: More details on the IC₉₉ results are provided in Section 1.2.1.1.

The solid lines represent for projected serum concentrations. The dashed lines represent for projected lung concentrations assuming 1% biodistribution. Please refer to the BGB-DXP593 Investigator’s Brochure for more detailed information on assuming 1% biodistribution.

Table 1: BGB-DXP593 Population PK Parameter Estimates in Cynomolgus Monkeys and Projected PK Parameters in Humans

Parameter (units)	Cynomolgus Monkey		Human Projection
	Estimate	%RSE	
CL (L/hr)	0.00068	4.9	0.0075
V _c (L)	0.121	3.9	2.96
Q (L/hr)	0.00299	7.5	0.033
V _p (L)	0.0984	3.8	2.41
IIV CL (%)	26.9	14.6	NA
IIV V _c (%)	24.1	13.5	NA
Residual variability (%)	14.2	5.1	NA

Abbreviations: CL, clearance; hr, hour; IIV, inter-individual variability; NA, not applicable; PK, pharmacokinetic; Q, intercompartmental clearance; RSE, relative standard error; V_c, volume of central compartment; V_p, volume of peripheral compartment.

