2.1.2. Secondary Objectives

- To characterize the pharmacokinetic (PK) profile of BGB-DXP593 administered intravenously as a single dose at each dose level in healthy subjects
- To evaluate the potential immunogenicity of BGB-DXP593 administered intravenously as a single dose at each dose level in healthy subjects

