5.2. Dosage, Administration, and Compliance

All eligible subjects will be assigned to one of the dose levels. Each subject will receive a single intravenous dose of BGB-DXP593 or matching placebo for 30-60 minutes. The dose of study drug will be based on the subject's actual body weight on the day of study administration.

As a routine precaution, subjects must be monitored for at least 2 hours after the infusion of study drug in an area with resuscitation equipment and emergency agents. The study drug must not be administered concurrently with any other drug.

For safety reasons, dose administration for the first 2 subjects randomized and dosed at each dose level will be monitored for at least 48 hours prior to the remaining subjects receiving the same dose level.

After the starting dose of study drug, the decision to proceed to each subsequent dose level will be made by the SMC at 7 days after the last subject at the current dose level has received the study drug, and all the safety, laboratory data have been reviewed.

Accurate records of the study drug received, dispensed, returned, and disposed of should be maintained in the site's Drug Inventory Log. Please refer to the Pharmacy Manual for details regarding study drug management, drug preparation, storage, and administration.

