8.3. Pharmacokinetic Assessment and Antidrug Antibody Testing

Blood will be collected to characterize the PK profile of BGB-DXP593 using validated immunoassays. Blood samples will be collected for characterization of ADA. Validated screening and confirmatory assays will be employed to detect ADAs in the samples. Samples collected for analyses of blood concentration may also be used to evaluate safety or efficacy aspects related to concerns arising during or after the study.

Blood sampling for PK and ADA will be collected at the timepoints specified in the PK and immunogenicity sampling schedule ([Appendix 3](#)).

The PK and ADA assays for BGB-DXP593 will be managed through a central laboratory. Refer to the laboratory manual for instructions regarding sample collection, handling, labeling, storage, and shipping of laboratory samples. The actual time of each sample collected will be captured to the nearest minute in the eCRF and recorded in the database.

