2. STUDY OVERVIEW

This is a first-in-human, randomized, double-blind, placebo-controlled, single dose escalation study to investigate the safety, tolerability, pharmacokinetic (PK), and immunogenicity of BGB-DXP593 in healthy subjects.

Two dose levels are planned for eligible subjects to receive a single intravenous dose of study drug (ie, BGB-DXP593 or placebo) at 10 mg/kg or 30 mg/kg, respectively. Another higher dose level will be allowed for dose escalation.

Enrollment will begin at the 10 mg/kg dose level. Escalation to the next dose level will occur 7 days after the last subject at the current dose level has received the study drug, and the safety, laboratory data have been reviewed.

At each dose level, eligible subjects will be randomized at a 3:1 ratio (6 active: 2 control) to the active arm for receiving BGB-DXP593 or to the control arm for receiving the same volume of placebo (ie, normal saline), respectively.

The sentinel dosing will be adopted for each dose level. In the other words, 2 eligible subjects will be randomized at a 1:1 ratio (1 active: 1 control) to receive BGB-DXP593 or placebo on Day 1; and the remaining subjects will be randomized at a 5:1 ratio (5 active: 1 control) to receive BGB-DXP593 or placebo at least 48 hours later, provided satisfactory safety and tolerability is demonstrated for the first 2 subjects randomized and dosed at the dose level.

Subjects are expected to be available for follow-up visits until Day 113 of the study. Subjects will be replaced if they cannot complete the infusion. Subjects may be replaced if they discontinue from the study before Day 29.

Subjects will be monitored for safety, tolerability, PK and immunogenicity of BGB-DXP593 throughout the study.

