6. STATISTICAL METHODS

6.1. Analysis Sets

The Safety Analysis Set will include all the subjects who received the study drug, and subjects will be grouped by actual treatment received. The Safety Analysis Set is used for all safety analyses.

The PK Analysis Set will include all the subjects who received the study drug and had any measurable concentration of study drug. The PK Analysis Set will be used for PK analyses.

BeiGene 12 May 2021

The ADA Analysis Set include all the subjects who received the study drug and in whom both baseline ADA and at least 1 postbaseline ADA results are available. The ADA Analysis Set is used for immunogenicity analyses.

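### SAP 6.7 lets a negative ADA result stand whatever drug level is in the sample; depending on an unstated assay drug tolerance, fewer draws may be readable at 30 than at 10 mg/kg (minor)

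*SAP*

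**What the plan says.** Protocol 2.1.2 gives as a secondary objective: "To evaluate the potential immunogenicity of BGB-DXP593 administered intravenously as a single dose at each dose level in healthy subjects". Immunogenicity is therefore to be read level by level.

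SAP 6.1 admits to the ADA Analysis Set dosed subjects "in whom both baseline ADA and at least 1 postbaseline ADA results are available". SAP 6.7 applies the same threshold to its ADA-evaluable subject and adds that results must be reportable, a term it does not define. A subject enters the numerator through "Treatment-induced ADA: ADA-evaluable subjects that were ADA-negative at baseline and ADA-positive following administration of biologic product", or through a titre rise of 4-fold or more from a positive baseline. The section also defines persistent, transient and neutralizing ADA. It has no inconclusive class and puts no drug-concentration condition on a negative.

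On the assays, Protocol 8.3 says "Validated screening and confirmatory assays will be employed to detect ADAs in the samples". Neither document states a drug tolerance. Protocol Appendix 3 schedules ADA samples predose and on Days 15, 29, 57, 85 and 113, with a PK sample at each of those times. SAP 6.7 permits further ADA analyses under a separate plan, but they are optional, and its example is the effect of ADA on PK and safety, not drug interference with the assay.

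**The concern.** Drug in a serum sample can bind ADA and keep an immunoassay from detecting it. This can turn a true positive into a negative but not the reverse, so any error lowers the reported incidence. Where it occurs, it grows with drug concentration and therefore with dose. Pooled placebo subjects carry no drug and are not affected.

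At stake is whether a negative means the same thing at each dose level. A subject whose only post-dose result was drawn early, with high drug in the sample, is counted as fully evaluable and negative. The PK sample that could qualify that result is already collected, but no rule uses it.

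**Working it through.** **Inputs.** Doses are "at 10 mg/kg or 30 mg/kg, respectively" (SAP 2). Infusion takes 30-60 minutes (Protocol 5.2); 1 h is used, and the choice hardly matters by Day 15. The dose depends on body weight: "The dose of study drug will be based on the subject's actual body weight on the day of study administration" (Protocol 5.2). No weight is fixed, so 70 kg is assumed, with 50-100 kg as a range. The projected human parameters in Protocol Table 1 are CL 0.0075 L/h, Vc 2.96 L, Q 0.033 L/h and Vp 2.41 L, for a two-compartment model with first-order elimination.

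**Step 1: reproduce Table 1.** The weight ratio implied by Vc is 2.96/0.121 = 24.46. Then CL = 0.00068 × 24.46^0.75 = 0.00748, Q = 0.00299 × 24.46^0.75 = 0.0329 and Vp = 0.0984 × 24.46 = 2.407. All agree with the table within 0.5%.

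**Step 2: half-life.** k10 = 0.0075/2.96 = 0.00253, k12 = 0.033/2.96 = 0.01115 and k21 = 0.033/2.41 = 0.01369 per hour. The rate constants α and β are ½[S ± √(S² − 4·k10·k21)], with S = k10 + k12 + k21 = 0.02738. This gives α = 0.02604 and β = 0.00133 per hour. The terminal half-life is ln 2/β, about 520 h or 21.7 days. Day 113 is 112 days after dosing, or 112/21.7 = 5.2 half-lives.

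**Step 3: drug at each ADA draw.** By Day 15 the α phase has gone, so C(t) ≈ Dose × [(k21 − β)/(α − β)]/Vc × e^(−βt). For 700 mg the leading factor is about 118 µg/mL. The full infusion solution at 70 kg gives, in µg/mL:

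| Dose | Day 15 | Day 29 | Day 57 | Day 85 | Day 113 |
|---|---|---|---|---|---|
| 10 mg/kg | 75.7 | 48.4 | 19.8 | 8.1 | 3.3 |
| 30 mg/kg | 227 | 145 | 59.3 | 24.2 | 9.9 |

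The ratio is 3.0 throughout, as linear kinetics require.

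**Step 4: readable draws.** A negative is taken as readable when drug is at or below the tolerance. The tolerance is an assumption, shown over its range (µg/mL):

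| Assumed tolerance | Readable at 10 mg/kg | Readable at 30 mg/kg |
|---|---|---|
| 1 | none | none |
| 5 | Day 113 | none |
| 10 | Days 85, 113 | Day 113 |
| 20 | Days 57, 85, 113 | Day 113 |
| 50 | Days 29 to 113 (4) | Days 85, 113 |
| 100 | all 5 | Days 57, 85, 113 |
| 150-200 | all 5 | Days 29 to 113 (4) |
| 230 or more | all 5 | all 5 |

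From about 3.3 up to 227 µg/mL, the 30 mg/kg count is always the lower one.

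**Step 5: sensitivity.** Holding the Table 1 parameters fixed and changing only the dose with weight, Day 113 drug over 50-100 kg is 2.4-4.7 µg/mL at 10 mg/kg and 7.1-14.1 at 30 mg/kg. Day 15 drug at 30 mg/kg and 100 kg is 324. Suppose the monkey between-animal variability in CL (26.9%) applied to humans: +2 SD is roughly CL × 1.7, and Day 113 falls to 0.31 against 0.92 µg/mL. With CL × 0.59 it rises to 14.4 against 43.2. With CL three times the projection it is 0.006 against 0.017, although Day 15 is still 28 against 85.

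**Step 6: early leavers.** Protocol 8.2.8 schedules a swab on Day 29 and discontinues a subject with a positive or suspected result; Protocol 7.6.2 asks for an EOS visit within 7 days. If that visit is on Day 36, drug is 48.4 × e^(−0.00133 × 168) ≈ 39 µg/mL at 10 mg/kg, and three times that, about 116, at 30 mg/kg. No later draw would exist for that subject.

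**The case against.** The strongest reply is that SAP 6.7 reports subjects, not draws. One positive at any of five draws is enough. Once tolerance exceeds about 10 µg/mL (about 14 at 100 kg), the Day 113 sample is readable at both doses, and ADA that persists to then is found in any completer. A reader might take the loss of draws in the working as an equal loss of incidence; the plan's definitions do not support that. Nor is it right that bias vanishes only when tolerance exceeds the Day 15 level. It is also absent at subject level when ADA lasts to a readable draw, and below about 3.3 µg/mL no draw is readable at either dose, so the difference in readable draws disappears.

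A reader might also infer that drug is certain to remain in every sample through follow-up. That rests on monkey-to-human scaling, and faster human clearance could nearly clear the late samples. It never applied to the predose draw or to placebo subjects.

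The undefined word reportable, the assay validation or the laboratory manual may already deal with high-drug samples; the documents do not say. ADA that speeds clearance would lower drug in the subjects concerned and reduce masking. ADA results and drug concentrations are both listed, so a reader who knew the tolerance could pair them. Subjects who leave before Day 29 may be replaced.

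All of this limits the size of the point. It does not supply a rule for when a negative can be relied on.

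**Conclusion.** The point stands as a minor one. SAP 6.7 has no drug-level condition on a negative ADA result, and the protocol's own projections put drug at all five post-dose draws in active subjects, about three times higher at 30 than at 10 mg/kg. The consequence depends on a tolerance that the documents do not give:

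- Between about 3 and 10 µg/mL, possibly no draw is readable at 30 mg/kg.
- Between about 10 and 227 µg/mL, Day 113 is readable at both doses, and the risk is mainly missed early or transient ADA and early leavers.
- At about 230 µg/mL or more for a 70 kg subject (about 325 at 100 kg), there is no masking at 10 or 30 mg/kg. A Dose Level C above 30 mg/kg would raise that threshold.

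The documents do not show that incidence is biased, nor that a fall in incidence with dose would be an artefact. Immunogenicity is a descriptive secondary objective with 6 active subjects per level and no planned test across levels, though one misread subject moves incidence by 1/6, or 17 percentage points. The figures assume linear kinetics, Table 1 parameters and 70 kg unless stated.

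**What to change.** In SAP 6.7:

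- State the validated drug tolerance of the ADA assay.
- Class a negative post-dose sample as inconclusive when its paired PK concentration is above that tolerance.
- Class a subject with no positive and no conclusive post-dose sample as inconclusive.
- Report positive, negative and inconclusive counts by dose level and by visit. The visit table is needed because a completer with a readable negative on Day 113 stays negative at subject level even if early samples were unreadable.
- Keep all ADA-evaluable subjects as the primary denominator, and give incidence as a range with inconclusive subjects counted as negative and then as positive.
- Do not report incidence among conclusive subjects alone. Positives count at any drug level while only high-drug negatives drop out, so it is biased upward. In an invented example with 1 positive, 3 negative and 2 inconclusive subjects, both truly negative, it gives 1/4 = 25% where the truth is 1/6 = 17%.
- List the paired drug concentration beside each ADA result.

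The cost is one extra category and one listing column. No sample or visit is added. Some subjects move from negative to inconclusive, and each widens the reported range by 1/6 at the planned size. If the tolerance proves high enough, no classification changes and the negatives are better supported.

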7.6.2. End-of-Study Visit

Subjects who permanently discontinue from the study will be asked to return to the study center for the End-of-Study (EOS) Visit, which is required to be conducted within 7 days after the premature study discontinuation. The Day 113 Visit is the EOS Visit for subjects who complete all the previously planned study visits.

If a subject refuses to return for the EOS Visit or is unable to do so, every effort should be made to contact the subject by telephone to determine their health status.

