8.4. Visit Windows

The PK sampling schedule allows for a visit window of ± 1 day for the visits at Day 15, Day 22 and Day 29, and a visit window of ± 2 days for the visits at Day 43, Day 57, Day 71, Day 85, and Day 113 ([Appendix 1](#) and [Appendix 3](#)). All assessments will be performed on the day of the specified visit.

8.5. **Unscheduled Visits**

Unscheduled visits may be performed at any time at the subject's or investigator's request if there are any safety concerns. The date and reason for the unscheduled visit must be recorded in the source documentation.

If an unscheduled visit is necessary to assess toxicity, then diagnostic tests may be performed based on the investigator's assessment as appropriate, and the results of these tests should be recorded on the unscheduled visit eCRF.

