APPENDIX 3. PHARMACOKINETIC AND ANTIDRUG ANTIBODY BLOOD SAMPLING

Study Day	Day 1			Day 2	Day 3	Day 4	Day 5	Day 8	Day 15	Day 22	Day 29	Day 43	Day 57	Day 71	Day 85	Day 113/ EOS
	0 (predose)	EOI	6	24	48	72	96	168	336	504	672	1008	1344	1680	2016	2688
Hours post the start of infusion	0 (predose)	EOI	6	24	48	72	96	168	336	504	672	1008	1344	1680	2016	2688
Window Period (hours)	-60 min to predose	Within 30 min after EOI	±2	±6	±6	±6	±6	±6	±24	±24	±24	±48	±48	±48	±48	±48
PK blood sampling	X	X	X	X	X	X	X	X	X	X	X	X	X	X	X	X
ADA sampling	X								X		X		X		X	X

Abbreviations: ADA, antidrug antibody; EOI, end of infusion; EOS, End-of-Study; min, minutes; PK, pharmacokinetics.

Note: Sample collection must be from the opposite arm that is used for study drug infusion. Refer to laboratory manual for detailed collection instructions.

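### SAP 6.7's 16-week rule for persistent ADA cannot be met on the planned sampling schedule, and subjects with two or more positives ending in a positive sample get no duration label

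*SAP*

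**What the plan says.** SAP 6.7 sorts treatment-induced ADA by duration, using two labels.

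- **Treatment-induced** applies to evaluable subjects "that were ADA-negative at baseline and ADA-positive following administration of biologic product".
- **Persistent** needs positives at two or more time points, follow-up included, where the first and last positives "are separated by a period of 16 weeks or longer".
- **Transient** has two limbs. One is a single positive time point in treatment or follow-up. The other is "or two or more time points during the treatment", less than 16 weeks apart, "and the subject last sampling time point is ADA-negative".

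There is no third duration category. The section opens with a caveat that "not all parameters described below may be derived", which it ties to the incidence and kinetics of the ADA detected.

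Protocol Appendix 3 schedules ADA sampling at predose and on Days 15, 29, 57, 85 and 113/EOS. Protocol 8.4 allows "a visit window of ± 1 day for the visits at Day 15, Day 22 and Day 29", and ± 2 days at Day 113. A subject who leaves early has an EOS visit, "which is required to be conducted within 7 days after the premature study discontinuation" (Protocol 7.6.2).

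**The concern.** The persistence threshold looks longer than the period over which post-dose ADA is sampled. If so, the persistent row of any duration table is zero whatever the drug does, and a reader could take that zero as evidence that ADA responses are short-lived.

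The two definitions also do not meet. Two or more positives less than 16 weeks apart, with the last sample still positive, satisfy neither. Detection of ADA over time is a secondary endpoint (SAP 4.2), and this is the only duration split that the SAP defines.

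**Working it through.** **Inputs.** Threshold: 16 weeks = 112 days (SAP 6.7). Post-dose ADA draws: Days 15, 29, 57, 85 and 113 (Protocol Appendix 3). Windows: ± 1 day at Day 15 and ± 2 days at Day 113 (Protocol 8.4). Early-termination EOS: within 7 days (Protocol 7.6.2).

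**Reproducing the schedule.** Hours = (Day − 1) × 24 gives 336, 672, 1344, 2016 and 2688, which match Appendix 3.

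**Longest interval between two post-dose positives.**

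| Case | Calculation | Days | Weeks |
|---|---|---|---|
| Nominal days | 113 − 15 | 98 | 14.0 |
| Window limits | 115 − 14 | 101 | 14.4 |
| Leaves on Day 115 without the Day 113 draw, EOS 7 days later (Day 122) | 122 − 14 | 108 | 15.4 |
| Required | 16 × 7 | 112 | 16.0 |

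Dose to Day 113 is 2688/168 = 16.0 weeks exactly. That interval cannot be used, because treatment-induced ADA requires a negative baseline, so the predose sample is never the first positive.

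**What would qualify.** Either a last draw on Day 14 + 112 = Day 126 or later, or an extra post-dose draw by Day 115 − 112 = Day 3 (by Day 122 − 112 = Day 10 if EOS is on Day 122). Neither is planned.

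**Completer patterns.** Five draws give 2⁵ − 1 = 31 patterns with at least one positive. Here *during the treatment* in the second limb of transient is taken to include follow-up.

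- Persistent: 0.
- One positive, not on Day 113: 4, transient.
- Two or more positives, Day 113 negative: 2⁴ − 1 − 4 = 11, transient.
- Two or more positives, Day 113 positive: 2⁴ − 1 = 15, no label.
- Positive only on Day 113: 1. It is transient if the negative-last-sample clause governs only the second limb, and unlabelled if the clause governs both.

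Total: 0 + 4 + 11 + 15 + 1 = 31.

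**Observed intervals in the 15 unlabelled patterns, by first positive.** Day 15: 98 days (14.0 weeks), 8 patterns. Day 29: 84 days (12.0 weeks), 4. Day 57: 56 days (8.0 weeks), 2. Day 85: 28 days (4.0 weeks), 1.

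**Literal reading of the transient limb.** Protocol 7.6 starts follow-up on the day after the infusion, so every planned post-dose ADA draw falls in follow-up. If *during the treatment* excludes follow-up, the 11 two-or-more-positive patterns ending in a negative lose their label too, and 15 + 11 = 26 of 31 are unlabelled.

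**The case against.** The best defence is that little depends on this split. SAP 6.7 commits to the number and percentage of subjects with detectable ADA and to the incidence of positive and neutralizing ADA. The duration labels appear only as definitions, with no table specified, and the section warns that some parameters may not be derived. With 6 active subjects planned per dose level, a reader can follow each ADA course in the listing. That stands, and it limits the point to a minor one. The caveat does not repair the definitions, though: it depends on what ADA is found, not on when samples are drawn, and it gives the omitted subjects no label.

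A second defence is that sampling can change. Protocol 3.2.2.1 lets times be added for later dose levels, and Protocol 8.5 allows unscheduled visits. A 16-week pair is therefore not impossible in every circumstance, only on the planned schedule.

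A reader might also infer that the unlabelled subjects are those with the longest responses. The documents do not support that. Three of the 15 unlabelled completer patterns span only 8 or 4 weeks, while a transient completer can span Day 15 to Day 85, which is 70 days (10.0 weeks). The gap arises from a positive last sample, not from the longest duration.

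**Conclusion.** The point holds and is minor. On the planned schedule the persistent category is empty by construction: at most 108 days are available against 112 required. Subjects with two or more positives including the last sample have no duration label.

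The count of 15 unlabelled completer patterns out of 31 assumes that the transient definition covers follow-up; on the literal reading it is 26. These are counts of possible patterns, not probabilities, because the documents give no ADA rate. If no subject becomes ADA-positive, nothing changes.

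A reader might infer that the immunogenicity results as a whole are compromised. They are not. Treatment-induced and treatment-emergent ADA incidence, neutralizing ADA incidence and the listings do not use the 16-week rule.

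**What to change.** Amend SAP 6.7 in three places.

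1. State that 16-week persistence cannot be reached on the planned schedule, so zero persistent subjects must not be read as evidence of short-lived ADA. Keep the persistent label for any subject whose actual samples show positives 16 weeks or more apart, for example after an added draw.
2. State that transient covers follow-up and EOS samples. Keep its less-than-16-weeks limit and its negative last sample, so that a 16-week pair followed by a negative is not relabelled transient.
3. Add one residual category, *ADA-positive at last available sample, 16-week persistence not evaluable*, for all other treatment-induced subjects whose last sample is positive. State whether a single positive at the last sample belongs there or in transient. For this category, report the observed first-to-last-positive interval and the day of the last sample, so that early leavers can be told apart from completers.

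Cost: a few lines of text, one extra category and, if a duration table is produced, a slightly different shell. No new samples or visits.
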